# 8. INTERIM ANALYSIS AND DATA MONITORING COMMITTEE REVIEW

There will be no interim read performed on this study.

# 9. SUBJECT INFORMATION

## 9.1. Disposition Information

Enrolled subjects will be allocated to one of the three mutually exclusive:

- 1. Completed: Subjects are considered to have completed the study if they (a) provided informed consent and/or assent; (b) they are eligible; (c) completed all three phases of testing; and (d) have not withdrawn/discontinued from the study.
- 2. Discontinued: Subjects are considered to have discontinued from the study if (i) test article was administered and (ii) discontinued from the study. Reasons for discontinuation include: (a) Adverse Event (b) unsatisfactory visual response due to test article (c) satisfaction lens fitting due to test article (d) lens discomfort (e) lens handling difficulties (e) withdrew consent during study (f) lost to follow-up (g) subject no longer meets eligibility criteria (h) subject withdrawn by PI to non-compliance to protocol (i) test article no longer available

- 3. Assigned and Test Article Administered: Total number subjects for which test articles were administered (Completed + Discontinued).
- 4. Enrolled but Not Dispensed: Subjects are considered to be Enrolled Not Dispensed Subjects if they were (i) enrolled to the study (provided informed consent and/or assent) but failed to satisfy the eligibility criteria (inclusion/exclusion criteria) or (ii) if they are randomized but did not receive a test article.
- 5. Total enrolled: Completed + Discontinued + Enrolled but Not Dispensed.

## 9.2. Protocol Deviations

Any protocol deviation that could impact the primary endpoints will result in the subject being excluded from the Per-Protocol analysis population. No analysis on protocol deviations will be performed. All reported protocol deviations will be listed.

## 9.3. Demographics and Baseline Characteristics

Demographic characteristics will be summarized by Per-Protocol, safety, and all enrolled population using descriptive statistics for continuous variables, and numbers and percentages of subjects for categorical variables. Demographic information will include age, gender, race, ethnicity and iris category.

# 9.4. Treatment Compliance and Extent of Exposure

Average daily wear time and average daily comfort wear time will be provided in the summary table. Non-compliance will be reported in protocol deviation.

# 9.5. Prior and Concomitant Medications

Prior and concomitant medications will be documented during screening and updated during the study when applicable. A listing for both prior and concomitant medications will be created for all enrolled subjects.

Disallowed medications for this study include: Estrogens, Antihistamines, Anticholinergics, Beta-blockers and Psychotropics.

Concomitant therapies that are disallowed include: Not applicable.

# 9.6. Medical History

A listing of medical and surgical history will be created for all enrolled subjects.

# 10. STATISTICAL ANALYSIS

## 10.1. Primary Analysis

Primary efficacy analysis:

All the efficacy analyses will be conducted on PP population. As sensitivity analysis, the efficacy analysis will be repeated on the ITT population

#### Visual Acuity

Distance monocular visual acuity (logMAR) will be tested under bright illumination bright contrast conditions at the 2-week follow-up evaluation and will be analyzed using a Bayesian normal random-effects model to compare the Test and Control lenses. The regression model will include lens type as the only fixed effect. Clinical site and subject will be included as random effects. Other subject characteristics such as gender and age will be included as fixed effects when appropriate.

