7.2. Detailed Study Procedures

VISIT 1

The subjects must present to Visit 1 wearing their habitual contact lenses.

	Visit 1: Screening			
Step	Procedure	Details		
1.1	Statement of Informed Consent	Each subject must read, understand, and sign the Statement of Informed Consent before being enrolled into the study. The Principal Investigator or his/her designee conducting the informed consent discussion must also sign the consent form.		
r.		Note : The subject must be provided a signed copy of this document.		
1.2	Demographics	Record the subject's date of birth, gender, race and ethnicity.		
1.3	Medical History and Concomitant Medications	Questions regarding the subjects' medical history and concomitant medications.		
1.4	Habitual Lenses	Questions regarding the subject's habitual lens type and parameters.		
1.5	Eligibility after Screening	All responses to Screening Inclusion Criteria questions must be answered "yes" and all responses to Exclusion Criteria must be answered "no" for the subject to be considered eligible.		

	Visit 1: Screening			
Step	Step Procedure Details			
		If the subject is deemed to be ineligible after screening, proceed to Final Evaluation and complete Subject Disposition. Refraction and Biomicroscopy forms are not required.		

	Visit 1: Baseline			
Step	Procedure	Details		
1.6	Baseline Questionnaire	The subject will respond to the CLUE Baseline Questionnaire.		
1.7	Entrance Visual Acuity	Record the distance Snellen visual acuity (OD, OS, and OU) to the nearest letter with their habitual contact lens correction in place. Subjects must read the smallest line until at least 50% of the letters are read incorrectly.		
1.8	Remove Habitual Lens	The subject's habitual lenses will be removed and stored in their own lens case. If they forgot to bring their lens case, one will be provided to them.		
1.9	Iris Color	The investigator will record the subject's iris color based on the scale provided.		
1.10	Keratometry	Record the keratometry readings OD and OS in diopters. This can come from any appropriate instrument so long as the same instrument is used at the Final Evaluation.		
1.11	Subjective Sphero- cylindrical Refraction	Complete subjective spherocylindrical refraction and record the resultant distance visual acuity (OD, OS, and OU) to the nearest letter. Best corrected distance visual acuity (BVA) must be 20/25+3 or better in each eye.		

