## 4. STATISTICAL HYPOTHESES FOR STUDY OBJECTIVES

#### 4.1. Primary Hypotheses

All the primary hypotheses must be met in order to satisfy the primary objective of this study.

- 1. Subjects wearing the JJVCI Investigational contact lenses on a daily wear basis will have patient reported comfort at the 2-Week Follow Up visit that is non-inferior to that of subjects wearing predicate device on a daily wear basis. A non-inferiority margin of -5 CLUE points will be used.
- 2. Subjects wearing the JJVC Investigational contact lenses on a daily wear basis will report distance monocular visual acuity (logMAR: bright room luminance / high contrast charts) at the 2-Week Follow Up visit that is non-inferior to that of subjects wearing predicate device on a daily wear basis. A non-inferiority margin of 0.05 LogMAR will be used.
- 3. Subjects wearing the JJVCI Investigational contact lenses on a daily wear basis will have patient reported outcome (Agree and Strongly Agree) on the Quality of Vision in Bright Light at the 2-Week Follow Up visit that is non-inferior to that of subjects wearing predicate device on a daily wear basis. A non-inferiority margin of 10% will be used.
- 4. Subjects wearing the JJVC Investigational contact lenses on a daily wear basis will have a percentage of any grade 3 or higher slit lamp findings at all visits (scheduled and unscheduled) that is non-inferior to that of subjects wearing predicate device on a daily wear basis. A non-inferiority margin of 5% will be used.
- 5. At least 90% of eyes wearing the JJVC Investigational contact lenses on a daily wear basis will have acceptable fits across the fitting and follow-up visits.

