#### 14. SAS CODE

### 14.1. Primary Endpoints

```
Distance Visual Acuity (logMAR)

PROC MCMC DATA =ads vp NTHREADS=8 SEED=20180906 NBI=100000 NMC=800000

THIN=100 DIAG=ALL OUTPOST= simout DIC PLOTS(SMOOTH FRINGE)=ALL

MCHISTORY=BRIEF PROPCOV=QUANEW STATS=ALL STATS(ALPHA = (0.05)

PERCENTAGE=(2.5 50 97.5))

plots(smooth) = all monitor = ( parms mu C mu T diff);
```

PARMS beta0 0; PARMS beta1 0 beta2 0 beta3 0 beta4 0; PARMS s2 1; PARMS s2g\_site 1 s2g\_subj 1;

```
PRIOR beta: ~ NORMAL(0, var = 1000);
PRIOR s2 ~ IGAMMA(.001, s =.001);
PRIOR s2g_site s2g_subj ~ IGAMMA(.001, s =.001);
```

```
RANDOM Gamma site ~ NORMAL(0, var = s2g site) SUBJECT=siteid;
RANDOM Gamma subj ~ NORMAL(0, var = s2g subj) SUBJECT=site subjid;
mu = beta0 + beta1*TRTAN + beta3*age +beta4*sexn + Gamma_site + Gamma_subj;
MODEL AVAL ~ normal(mu, var = s2);
```

```
BEGINNODATA;
```

```
mu C = beta0 + 0.5* beta4;
mu T = beta0 + beta1 + 0.5* beta4;
diff = mu T - mu_C;
ENDNODATA;
RUN;
```

```
Where,
ads vp =analysis data set for Distance Monocular Visual Acuity (logMAR)
trtan= numerical representation of treatment, where Test=1 and Control=0
bASE= Baseline CLUE comfort score
age= Age of subject at time of consent
sexn= Numerical representation of sex, where Female=1 and Male=0;
siteid= Site Number
site_subjid=Unique Subject ID
```

```
CLUE Comfort
```

```
PROC MCMC DATA = ads cmt NTHREADS = 8 SEED=198756325 nbi=100000 nmc
=800000 thin=100 DIAG =ALL OUTPOST=simout DIC PLOTS(SMOOTH FRINGE)= ALL
MCHISTORY = BRIEF PROPCOV =QUANEW STATS=ALL STATS(ALPHA=(0.05)
PERCENTAGE=(2.5 50 97.5))plots(smooth)=ALL MONITOR=(_parms_mu_C mu_T diff);
PARMS beta0 60;
```

```
CR-6305, Statistical Analysis Plan Version 1.0
```

PARMS beta1 0 beta2 0 beta3 0 beta4 0; PARMS s2 400; PARMS s2g\_site 1;

PRIOR beta: ~ NORMAL(0, var = 1000); PRIOR s2 ~ IGAMMA(.001, s =.001); PRIOR s2g\_site ~ IGAMMA(.001, s =.001);

random Gamma\_site ~ NORMAL(0, var = s2g\_site) SUBJECT=SITEID;

mu = beta0 + beta1\*TRTAN + beta2\*base + beta3\*age + beta4\*sexn + Gamma\_site;

```
MODEL AVAL ~ normal(mu, var = s2);
```

```
BEGINNODATA;
mu C = beta0 + 0.5* beta4;
mu T = beta0 + beta1+ 0.5* beta4;
diff = mu_T - mu_C;
ENDNODATA;
RUN;
```

Where, ads\_cmt=analysis data set for CLUE Comfort trtan= numerical representation of treatment, where Test=1 and Control=0 bASE= Baseline CLUE comfort score age= Age of subject at time of consent sexn= Numerical representation of sex, where Female=1 and Male=0; siteid= Site Number

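### The primary logMAR model leaves out the per-eye baseline acuity already recorded at Visit 1, a cheap gain in precision on a must-pass endpoint

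*SAP*

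**What the plan says.** SAP 10.1, Visual Acuity, describes a Bayesian normal model with "lens type as the only fixed effect" and random effects for site and subject. It then adds: "Other subject characteristics such as gender and age will be included as fixed effects when appropriate". The equation contains lens, subject and site only. The code in SAP 14.1 settles the covariates as age and sex: "mu = beta0 + beta1*TRTAN + beta3*age +beta4*sexn + Gamma_site + Gamma_subj". That code declares a coefficient beta2 that never enters the mean. The variable key below it lists "bASE= Baseline CLUE comfort score", which is not an acuity and is not in the model either.

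A baseline acuity exists. At Visit 1, step 1.11, Protocol 7.2 tells the investigator: "Complete subjective spherocylindrical refraction and record the resultant distance visual acuity (OD, OS, and OU) to the nearest letter". Best-corrected acuity there "must be 20/25+3 or better in each eye". SAP 2.4 requires baseline information to be collected before randomization, and the lens is assigned later, at step 1.14.

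The SAP text does use baseline values for two other primary endpoints in 10.1: CLUE comfort and slit lamp findings.

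On the role of this endpoint, SAP 4.1 states: "All the primary hypotheses must be met in order to satisfy the primary objective of this study". For acuity: "A non-inferiority margin of 0.05 LogMAR will be used".

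**The concern.** An eye's best-corrected acuity before lens wear is the natural predictor of its acuity through a study lens two weeks later. When such a value is measured before randomization on every eligible subject, conditioning on it removes between-subject variance from the treatment comparison and corrects for chance imbalance between arms. The plan does this for comfort, but not for acuity.

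What is at stake is precision. All five primary hypotheses must be met, so a miss on acuity through a needlessly wide interval would fail the study's primary objective. The allowance for other characteristics when appropriate does not close the gap. It does not name baseline acuity, and a covariate on a confirmatory endpoint should be fixed before the data are seen.

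**Working it through.** **Inputs from the documents.** Margin 0.05. Decision on the upper limit of a two-sided 95% credible interval, treated here as one-sided 0.025. Planned completers 112 per arm. Assumed difference 0.02 logMAR, sign not stated (SAP 7.4). Historical SDs 0.0862 (Test) and 0.0740 (Control), SAP Table 7. Planning matrix: variances 0.004047 and 0.004737, covariance 0.002894.

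**Inputs assumed.** Test truly 0.02 worse, so the distance to the margin is 0.05 − 0.02 = 0.03. The matrix correlation, 0.002894 / √(0.004047 × 0.004737) = 0.66, is taken as the correlation between eyes. The correlation r of baseline acuity with two-week logMAR is in neither document, so a range is shown.

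**The plan's own figure: 30 subjects, 86%.** Two readings of the matrix come close.
- Paired: SD of a difference = √(0.004047 + 0.004737 − 2 × 0.002894) = 0.0547. SE = 0.0547/√30 = 0.00999. Power = Φ(0.03/0.00999 − 1.96) = 85.1%.
- Parallel, two eyes averaged, 15 per arm, 0.02 in favour of Test (distance 0.07): 86.6% by noncentral t.

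A parallel reading with 0.02 against Test gives about 27% at 15 per arm (normal approximation). The documents do not say which was used, so this figure does not settle the power of the present design.

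**SD of a subject's two-eye mean.**
- A, Table 7 SDs: pooled SD = √((0.0862² + 0.0740²)/2) = 0.0803; eye mean = 0.0803 × √((1 + 0.66)/2) = 0.0732.
- B, planning matrix: √((0.004047 + 0.004737 + 2 × 0.002894)/4) = 0.0604.
- C, Table 7 SDs with eyes fully correlated: 0.0803.

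**Power at 112 per arm.** SE = SD × √(1 − r²) × √(2/112), with noncentral t on 222 df.

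| Test 0.02 worse | r = 0 | 0.1 | 0.2 | 0.3 | 0.5 |
|---|---|---|---|---|---|
| A: SD 0.0732 | 86.3% | 86.6% | 87.6% | 89.3% | 94.1% |
| B: SD 0.0604 | 95.9% | 96.1% | 96.6% | 97.3% | 99.0% |
| C: SD 0.0803 | 79.5% | 79.9% | 81.1% | 83.1% | 89.5% |

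In case A the unadjusted SE is 0.0732 × √(2/112) = 0.00978 and the 95% half-width is 0.0193. At r = 0.5 the half-width falls to 0.0193 × √0.75 = 0.0167.

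**If Test is not worse.** With no true difference (distance 0.05), unadjusted power is 99.9% in case A, essentially 100% in B and 99.6% in C. With Test 0.02 better it is essentially 100% throughout. The historical means point this way: −0.088 − (−0.0622) = −0.026, and a negative difference favours Test.

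**The case against.** The strongest reply is that nothing here is wrong. Subjects are randomized, the comparison without baseline acuity is valid, and neither document promises this adjustment. That stands in full. A reader might infer from the omission that the acuity result would be biased; randomization rules that out.

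A reader might also infer that the endpoint is underpowered. The documents do not support this. The SAP gives the 0.02 no sign, and its historical means favour Test. Even with Test worse, case A exceeds the planned 80%. Only the extreme case C falls just below it.

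The size of the gain is also soft:
- The 0.66 is not documented as a between-eye correlation. Protocol 14.2 describes it as a correlation across study periods, and the SAP says only within the same subject. Case A also combines it with SDs larger than the matrix's own (about 0.064 and 0.069).
- r may be low. The baseline is a Snellen acuity through refraction, cut off by eligibility. Step 1.11 has no instruction to read on until half the letters are missed, unlike steps 1.7, 1.21 and 2.6, so a ceiling is possible. The outcome is an ETDRS score through the lens. At r = 0.1–0.2 the gain in case A is about one point or less.

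The phrase about lens as sole fixed effect must be read with the sentence after it and with the code, which add age and sex. The unused beta2 might suggest that a baseline acuity term was intended and then dropped. The key names a CLUE comfort score instead, so a carry-over from the comfort code is the likelier explanation.

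What survives is narrow: a relevant pre-randomization value is collected and not pre-specified, and using it costs almost nothing.

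**Conclusion.** The point holds as a small, optional gain in precision. Baseline acuity is absent from the SAP text, equation and code for a must-pass endpoint, although it is recorded per eye before randomization.

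The benefit is conditional. If Test is truly one letter worse and the Table 7 SDs apply, with 0.66 between eyes, power rises from about 86% to 89% at r = 0.3 or 94% at r = 0.5, and hardly at all at r = 0.1. Under the planning-matrix variances it starts at about 96%. If Test is equal or better, the adjustment only narrows the interval. The sign of the difference, the between-eye correlation and r are all assumptions. Rating: free improvement, nice to have.

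**What to change.** Before database lock:
1. In SAP 10.1, Visual Acuity, name per-eye baseline best-corrected distance acuity (Visit 1, step 1.11), in logMAR, as a fixed covariate in the text and the equation.
2. State the rule that turns a Snellen line-plus-letters score into logMAR. The SAP formula covers only a change of ETDRS test distance.
3. In the SAP 14.1 acuity code, let beta2 multiply this covariate, and replace the CLUE comfort entry in the key with the baseline acuity. The monitored difference is still beta1, so the decision rule does not change.

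The cost is one sentence, one conversion rule and one code term. No new data or visits are needed, and a weak covariate costs one parameter.

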#### The Model:

Let  $y_{ijkl}$  the visual acuity (logMAR) for the  $l^{th}$  subject at the  $k^{th}$  site, assigned to the  $i^{th}$  lens for the  $j^{th}$  eye. The likelihood for  $y_{ijkl}$  is constructed as follows:

Where,

 $y_{ijkl} \sim N(\mu_{ijkl}, \sigma_{ijkl}^2)$ 

 $\mu_{ijkl} = \mu_0 + \beta_1 Lens_i + \gamma_{l(k)} + \alpha_k$ 

In this model, lens we define  $Lens_i=0$  for the Control lens and  $Lens_i=1$  for the Test lens. So  $\beta_1$  stands for the difference between the Test and Control lens with respect to logMAR visual performance. A negative  $\beta_1$  indicates the Test performed better than the Control lens.

We assume random subject effects are independent and identically distributed (i.i.d) as  $\gamma_j \sim N(0, \sigma_{subject}^2)$  as random subject and, the random site effect is i.i.d as  $\alpha_k \sim N(0, \sigma_{site}^2)$  for i=1,2 (lens), j=1, 2 (eye), k=1, 2, 3, 4, 5, 6 (site).

For the  $\beta$  coefficients, independent non-informative priors N(0, 1000) will be used. For the variance of random effects  $\sigma_{subject}^2$  and  $\sigma_{site}^2$  independent non-informative conjugate priors inverse-gamma(0.001, 0.001) will be used. For  $\sigma_{ijkl}^2$ , non-informative conjugate priors inverse-gamma(0.001, 0.001) will be used where  $\sigma_{ijkl}^2$ , is the variance of  $y_{ijkl}$ . The metropolis sampler algorithm as implemented in the SAS/STAT MCMC 14.2 procedure will be used to estimate the posterior distribution of the unknown parameters. Inferences will be made based on the 95% posterior credible intervals for relevant parameters.

Hypothesis Testing

The null and alternative hypothesis for visual acuity (logMAR) to test for non-inferiority of the Test lens relative to the Control lens is as follows:

$$H_0: \beta_1 \ge 0.05$$
  
 $H_A: \beta_1 < 0.05$ 

Non-inferiority will be declared if the upper limit of the 95% credible interval of the difference between the Test and Control is below 0.05, i.e.  $P(\beta_1 < 0.05) \ge 0.975$ .

### **CLUE Overall Comfort**

CLUE Comfort scores will be analyzed using a Bayesian normal random-effects model to compare the Test and Control lenses at the 2-week follow-up evaluation. The regression model will include baseline CLUE comfort scores and lens type as fixed effects. Clinical site will be included as random effects. Other subject characteristics such as age, gender, race and iris category will be included as fixed covariates when appropriate.

The Model:

Let  $y_{ijk}$  denote the CLUE Comfort score for the  $k^{th}$  subject at the  $j^{th}$  site, assigned to the  $i^{th}$  lens. The likelihood for  $y_{ijk}$  is constructed as follows:

$$y_{ijk} \sim N(\mu_{ijk}, \sigma_{ijkl}^2)$$

Where

$$\mu_{ijkl} = \mu_0 + \beta_1 Lens_i + \beta_2 baseline + \gamma_j$$

In this model, we define  $Lens_i=0$  for the Control lens and  $Lens_i=1$  for the Test lens. So  $\beta_1$  stands for the difference between the Test and Control lens with respect to CLUE comfort; A positive  $\beta_1$  indicates the Test performed better than the Control.

We assume random site effects are independent and identically distributed (i.i.d) as  $\gamma_j \sim N(0, \sigma_{sits}^2)$  for site for j=1, 2, 3, 4, 5, 6 (site).

For the  $\beta$  coefficients, independent non-informative priors N(0, 1000) will be used. For the variance of random effect of  $\sigma_{site}^2$  an independent non-informative conjugate prior, inverse-gamma(0.001, 0.001) will be used. Starting values for the mean and variance of CLUE scores will be 60 and 400 (since standard deviation of CLUE is normalized to be 20), respectively. The Metropolis sampler algorithm as implemented in the SAS/STAT MCMC 14.2 procedure will be used to estimate the posterior distribution of the unknown parameters. Inferences will be made based on the 95% posterior credible intervals for relevant parameters.

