## 7.5. Statistical Significance Level

All planned analysis will be conducted with an overall type I error rate of 5%. There will be neither adjustment for multiple tests nor adjustment for multiplicity of endpoints. Unless otherwise specified, all statistical tests will be 2-sided.

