## **CLUE Overall Quality of Vision and Handling**

CLUE Overall Quality of Vision and Handling will be analyzed using the same statistical method described for CLUE Overall Comfort.

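### The CLUE comfort program also puts its mean-0, variance-1000 prior on the uncentred intercept, which on average nudges the lens difference towards Test and raises the one-sided error from 2.5% to about 2.6–3.1%

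*SAP*

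**What the plan says.** SAP 10.1, CLUE Overall Comfort, models the two-week score as μ0 plus a lens effect β1, a baseline term and a random site effect. Of the model it says "The regression model will include baseline CLUE comfort scores and lens type as fixed effects"; age, sex and other characteristics may be added. For the β coefficients, "independent non-informative priors N(0, 1000) will be used". No prior is stated for μ0. Protocol 14.5 has the same wording.

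The CLUE Comfort program in SAP 14.1 names the intercept beta0 and has a single prior statement for everything that begins with beta: "PRIOR beta: ~ NORMAL(0, var = 1000". This shows that 1000 is a variance. The only other priors in that program are for the two variances, so beta0 has no prior of its own. Baseline, age and sex enter with no centring stated, and the lens coding is given as "trtan= numerical representation of treatment, where Test=1 and Control=0".

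The number 60 appears only as a starting value. The text says "Starting values for the mean and variance of CLUE scores will be 60 and 400" and the code has "PARMS beta0 60". That does not move the prior mean, which stays at zero.

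Comfort passes if P(β1 > −5) is at least 0.975, and all five primary hypotheses must be met (SAP 4.1). SAP 10.2 extends the method: "CLUE Overall Quality of Vision and Handling will be analyzed using the same statistical method" as comfort. SAP 14.2 reuses the code.

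**The concern.** A normal prior with variance 1000 is vague for a logMAR difference. It is not vague for the level of a CLUE score: the scale has population mean 60 and SD 20, and the historical comfort means are 63.90 (Control) and 66.66 (Test). A raw mean of 60 to 64 lies 60/31.6 = 1.9 to 64/31.6 = 2.0 prior SDs from the prior mean.

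Because Control is coded 0, the estimates of the intercept and of β1 are negatively correlated. If the prior drags a positive intercept towards zero, β1 rises, and that favours Test. At a true difference of −5, the prior on β1 itself adds a little in the same direction. At stake is the error rate of a must-pass non-inferiority test whose prior is labelled non-informative. The SAP gives no operating characteristics that would reveal the effect.

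**Working it through.** **Plan's own figure.** The plan gives no error rate for the Bayesian comfort rule, so there is none to reproduce. Its 87% power for comfort does not involve the prior and is a separate matter.

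**Inputs from the documents.** 112 completers per arm; SD 21; margin −5; posterior threshold 0.975; prior variance 1000; Control = 0 and Test = 1; historical Control mean about 64.

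**Assumptions not in the documents.** Baseline mean 62; equal SDs at baseline and follow-up, so that the baseline slope equals the correlation r; no age or sex effect in the main calculation; r between 0 and 0.7.

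**Formulas.** Residual variance: σe² = 441 × (1 − r²). Uncentred intercept: μ0 = 64 − 62r. The covariance of the intercept and β1 is about −σe²/112, and Var(β1) = 2σe²/112. To first order, at a true −5:

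- shift from the intercept prior ≈ (σe²/112) × μ0/1000
- shift from the prior on β1 ≈ 5 × Var(β1)/1000
- one-sided error ≈ Φ(−1.96 + shift/SE), where SE = √Var(β1)

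| r | σe²/112 | μ0 | SE | intercept part | β1 part | total shift | error |
|---|---|---|---|---|---|---|---|
| 0 | 3.94 | 64.0 | 2.81 | 0.252 | 0.039 | 0.291 | 3.2% |
| 0.3 | 3.58 | 45.4 | 2.68 | 0.163 | 0.036 | 0.199 | 3.0% |
| 0.5 | 2.95 | 33.0 | 2.43 | 0.097 | 0.030 | 0.127 | 2.8% |
| 0.7 | 2.01 | 20.6 | 2.00 | 0.041 | 0.020 | 0.061 | 2.7% |

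The first-order form slightly overstates the pull, because the divisor should be 1000 plus the sampling variance of the intercept.

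**Simulation.** The model had an intercept, lens, raw baseline, raw age and sex, and the true difference was −5. Mean shifts were 0.28, 0.19, 0.12 and 0.06 for the four values of r. One-sided error was about 3.1%, 2.9%, 2.7% and 2.6%, against about 2.5% with flat priors. At r = 0, 0.3 and 0.5 there were 30,000 trials each. With a prior variance of 1,000,000 the shift was 0.0003 or less and the error rate matched the flat prior.

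**With random site effects.** A closed-form calculation with 10 sites gave shifts of 0.12 to 0.24 points and errors of 2.8–3.0% for intercepts of 32 to 54. A Gibbs run with unknown variances (3,000 trials per setting, paired) gave mean shifts of 0.16 and 0.21 points, and errors of 2.8% and 2.9% against 2.6% flat. The Monte Carlo error of one such rate is √(0.026 × 0.974/3000) = 0.3 percentage points, so the paired shifts are the firmer evidence from that run.

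**Sensitivity to the slopes.** A steep age slope brings the uncentred intercept to zero or below. With r = 0.7 and an age slope of 0.7 points per year, the mean shift was about +0.01 and 24% of simulated trials moved away from Test. With an intercept of about −8, the pull was negative in 19% of randomisations and the error was 2.5%.

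**Centring alone.** With centred covariates the intercept is about 64 at every r. The total shift is then 3.58 × 0.064 + 0.036 = 0.26 at r = 0.3, 2.95 × 0.064 + 0.030 = 0.22 at r = 0.5, and 2.01 × 0.064 + 0.020 = 0.15 at r = 0.7. Each is larger than the uncentred value.

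**The case against.** The strongest reply is that this hardly matters. A shift of 0.1 to 0.3 points compares with a posterior SD of roughly 2 to 3 points and a 5-point margin. It changes the result only when the credible bound falls within that sliver of −5. SAP 7.5 states "All planned analysis will be conducted with an overall type I error rate of 5" per cent, so an error of about 3% still lies below 5% if that figure is read as one-sided. The all-must-pass rule lowers the chance of false overall success further. The prior's value is also printed openly. All of this stands as to size. It does not remove the pull on the comfort estimate, and the declared 0.975 rule implies 2.5%, not 5%.

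The upper end of the range rests on r = 0, which is unlikely for the same scale in the same person two weeks apart. That also stands, and it is why the range is carried down to r = 0.7.

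A reader might infer that the lens difference is always pulled towards Test, whatever the data. The documents do not support that. Sign and size depend on baseline and age slopes that they do not give, and on chance imbalance between the arms. When the estimate of β1 is positive, as the planned 2-point advantage would have it, the prior on β1 itself works against Test. A reader might also take the intercept to be 1 to 2 prior SDs from zero. That fits the raw mean and moderate baseline slopes, but r = 0.7 gives 20.6/31.6 = 0.65 SD, and steeper slopes give less.

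Finally, the SAP text alone does not show the defect, because it sets no prior on μ0. Only the code does.

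**Conclusion.** The point holds in a limited form. As coded, the comfort model places an informative prior on its intercept, and the text is silent on that prior. For plausible positive intercepts the average effect at a true −5 is about 0.06 to 0.28 points towards Test, which is roughly 1% to 6% of the margin. The one-sided error is then about 2.6–3.1% instead of 2.5%. These figures assume 112 per arm, SD 21, a baseline mean of 62, a Control mean of 64 and r from 0.7 down to 0, with no age effect. With steep baseline and age slopes the average effect disappears, and individual trials can move the other way.

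This is a minor correction. It is worth making because the test is must-pass and the prior is described as non-informative. Handling and vision inherit the code, and their historical means of 64 to 71 put them in the same position.

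**What to change.** In SAP 10.1, CLUE Overall Comfort (and by reference Overall Quality of Vision and Handling), state a prior for μ0 explicitly. Use a variance of 1,000,000 for the intercept and the β coefficients. Change the prior line in the 14.1 comfort code to `PRIOR beta: ~ NORMAL(0, var = 1e6)`, so that text and code agree. A prior centred at 60 with the same large variance would serve equally well for the intercept. Centring baseline and age may help mixing, but it does not remove the shift by itself. The priors of the other models need not change for this reason.

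The cost is one number in the text and one line of code, with no extra data or subjects. The only downside is a very slightly less favourable posterior for the Test lens.
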